### **3.2 INDEPENDENT REVIEW FACILITY**

Details are included in the project SAP, Section 3.2.

### **3.3 DATA MONITORING**

Details are included in the project SAP, Section 3.3.

## **4. STATISTICAL METHODS**

### **4.1 ANALYSIS POPULATIONS**

#### **4.1.1 Induction Phase**

##### **4.1.1.1 Open-Label Induction (OLI) Population**

Patients enrolled into the Induction Phase who received study drug will be summarized under the OLI population for all efficacy summaries.

##### **4.1.1.2 OLI Histology Evaluable Population**

The histology evaluable patients will include all patients in the OLI population who provided a baseline histology sample. Patients with absence of baseline neutrophilic inflammation defined by a Nancy Histology Index (NHI)  $\leq$  1 will be excluded.

##### **4.1.1.3 Safety Population**

The safety analysis population for the Induction Phase will include all patients who received at least one dose of etrolizumab during the Induction Phase.

#### **4.1.2 Maintenance Phase**

##### **4.1.2.1 Modified Intent-to-Treat (mITT) Population**

Efficacy analyses for the Maintenance Phase will be performed using a modified intent-to-treat (mITT) analysis population (with the exception of histologic remission). This analysis population will include patients randomized in the Maintenance Phase who received at least one dose of maintenance study drug. Patients will be grouped according to the treatment assigned at maintenance randomization.

To allow consistency across the program the mITT population is being used. This differs to terminology in the Protocol Version 7, Section 6.4, which uses intent-to-treat population.

#### **4.1.2.2 Pharmacokinetic (PK)-Evaluable Population**

The PK-evaluable population includes patients who have received at least one dose of study drug and have at least one quantifiable concentration measured during the Maintenance Phase.

#### **4.1.2.3 Histology-Evaluable Population**

The histology-evaluable patients will include all patients in the maintenance mITT population, who have documented neutrophilic inflammation at baseline. For the main analysis based on NHI, neutrophilic inflammation is characterized by NHI greater than 1. Sensitivity analyses will be based on the Robarts Histopathological Index (RHI) and Geboes Grading Scale. Definitions for neutrophilic inflammation and histologic remission under these alternative histologic scoring systems are provided in Table 3 of the project SAP.

#### **4.1.2.4 Safety Population**

The safety analysis population for the Maintenance Phase will include all patients who receive study drug in the Maintenance Phase. Patients will be included in the treatment arm for the treatment most frequently received during the Maintenance Phase.

### **4.2 ANALYSIS OF STUDY CONDUCT**

All data available in the database up to the point the last patient has completed their Week 62 visit will be included to evaluate study conduct. This will include all available data from the Induction and Maintenance Phases at the time of cutoff for the primary analysis. The following analyses will be performed to evaluate the study conduct:

- Summary of protocol deviations
- Summaries of mITT, histology-evaluable, PK-evaluable, and safety populations, including numbers of patients in each population
- Summary of patient disposition, including the number of doses received, reasons for patients withdrawing from the study and from study treatment, and number of patients taking study treatment.

### **4.3 ANALYSIS OF TREATMENT GROUP COMPARABILITY**

Details are included in the project SAP, Section 4.3.

### **4.4 EFFICACY ANALYSIS**

All statistical hypotheses for the primary and key secondary endpoints will be evaluated under a multiple testing procedure to ensure an overall type I error no greater than 5%. Details on this testing procedure are provided in Section [4.4.3](#).

Statistical comparisons will only be conducted in the Maintenance Phase. Efficacy data collected during the Induction Phase will be summarized descriptively.

All comparisons between the etrolizumab and placebo arms for binary data will use the CMH test statistic stratified by the three IxRS stratification factors (Disease activity at screening [MCS  $\leq$ 9/MCS  $\geq$ 10], Concomitant treatment with CS at baseline [yes/no], Concomitant treatment with IS after Week 10 [yes/no]) as described in Section 3.1.1. For all analyses in the Induction and Maintenance Phases, where comparisons back to baseline are made, baseline is defined as the last available assessment prior to first receipt of study drug in the Induction Phase.

In alignment with the addendum to ICH E9, the primary efficacy treatment effect (estimands) is described for the primary treatment effect in Section 4.4.1.1. The estimand attributes include the following two intercurrent events: treatment discontinuation and use of rescue medication as described below:

- **Treatment discontinuation:** All patients who discontinue study drug during the treatment period of the Maintenance Phases will not be assessed for any future Week 62 endpoints. Therefore, these patients will be assumed to be non-responders in the categorical endpoints analyses. For continuous endpoints (e.g., IBDQ, UC-PRO/SS) these patients' data will be set to missing. Handling of missing data is described in the project SAP, Section 4.8.
- **Use of rescue therapy:** Increased or new background medications compared to baseline for the treatment of UC is considered rescue therapy. Rescue therapy use is described in the protocol and also summarized in Appendix 3. All patients receiving permitted rescue therapy during the Maintenance Phases will be asked to continue the study through endpoint assessment and safety follow-up. All patients receiving prohibited rescue therapy during the Maintenance Phases will be asked to enter safety follow-up, with no assessment of any future Week 62 endpoints. Patients who receive rescue therapy (be it permitted or prohibited) during the Induction Phase are not eligible to enroll in the Maintenance Phase. Patients who receive (permitted or prohibited) rescue medication will be considered non-responders in the primary analysis for all time points following the time they received rescue therapy. For continuous outcomes (e.g., IBDQ, UC-PRO/SS), scores collected after the first use of rescue medication will have their data imputed using the worst post-baseline score from the following assessments: (the last score available prior to the start date of first rescue medication and all scores available after the start date of rescue medication use).

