## **2.2 OUTCOME MEASURES**

Baseline throughout this document is defined as the last available assessment prior to first receipt of study drug in the Induction Phase. The efficacy outcome measures listed below deviate from the current Study GA29102 Protocol Version 7. The current protocol includes change from baseline in stool frequency (SF) and rectal bleeding (RB) at Week 6 as secondary outcomes measures, and endoscopic remission at Week 10, histologic disease activity change from baseline to Week 10, improvement in the endoscopic mucosa at Week 10, and change in health utilities, as assessed by the EuroQoL Five-Dimension Questionnaire (EQ-5D) from baseline to Week 10 as exploratory outcome measures. These outcomes measures cannot be analyzed due to no comparator arm at Week 6 or Week 10; therefore, they have been removed from the list below. The safety and pharmacokinetic (PK) measures can be found in the Protocol Synopsis in [Appendix 1](#).

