### Appendix 3 Rescue Therapy

Study Phase	Type	Description
Induction	Permitted	Initiation or escalation beyond baseline dose of the following agents for the treatment of worsening UC symptoms. 
 
Immunosuppressants (AZA, 6-MP or MTX)
 
Oral or topical 5-ASA or corticosteroid (use of topical at baseline is among the exclusion criteria; rectal is synonymous with topical)
 

	Prohibited	Any use of other immunosuppressants, including: 
 
TNF inhibitors and biosimilars thereof
 
Cyclosporine, tacrolimus, sirolimus, or MMF
 
Anti-adhesion molecules, including natalizumab and vedolizumab
 
Other biologics, such as efalizumab, alemtuzumab, visilizumab and rituximab
 
Other investigational agents, including vaccines (e.g., MAP or ChAdOx2 HAV, JAK inhibitors))
 

Maintenance	Permitted	Same definition as induction, noting that: 
 
Maintenance period begins with an oral corticosteroid taper
 
All patients receiving rescue therapy during the induction period are ineligible to enter maintenance
 

	Prohibited	Same definition as induction, noting that: 
 
All patients receiving rescue therapy during the induction period should withdraw from the study
 

5-ASA=5-aminosalicylic acid; 6-MP= 6-mercaptopurine; AZA=azathioprine; ChAdOx2 HAV=chimpanzee adenovirus Oxford 2 hepatitis A vaccine; JAK= Janus kinase; MAP=Mycobacterium avium subspecies paratuberculosis; MMF=mycophenolate mofetil; MTX=methotrexate; TNF=tumor necrosis factor; UC=ulcerative colitis.

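### SAP 4.4's rescue rule, applied as written, does not count a steroid restart after a completed taper as rescue when the dose is at or below the entry dose

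*SAP*

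**What the plan says.** Rescue use is one of the two intercurrent events of the primary estimand (SAP 4.4.1.1). SAP 4.4 makes a patient who receives rescue, permitted or prohibited, a non-responder at every later time point. The defining sentence reads "Increased or new background medications compared to baseline for the treatment of UC is considered rescue therapy". The reference point is set in SAP 2.2: "Baseline throughout this document is defined as the last available assessment prior to first receipt of study drug in the Induction Phase".

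SAP 4.4 then adds: "Rescue therapy use is described in the protocol and also summarized in Appendix 3". In the induction row, Appendix 3 defines permitted rescue as "Initiation or escalation beyond baseline dose of the following agents for the treatment of worsening UC symptoms", and corticosteroids are among the agents listed. The maintenance row says "Same definition as induction, noting that" and then observes "Maintenance period begins with an oral corticosteroid taper". It does not classify a steroid restarted after that taper is over.

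The protocol says three relevant things:
- Section 6.4 makes a maintenance patient a non-responder for starting a corticosteroid for UC, with no dose threshold. A dose increase over baseline is a separate criterion.
- Section 3.1.1.2 says that going back up to the baseline dose is not rescue if it happens during the taper.
- The same section lists, among the rescue situations, oral steroids above 10 mg for 5 days or longer in patients who have completed the taper.

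**The concern.** All baseline steroid users who enter maintenance are meant to taper to zero from Week 10. The comparison that matters for them is with their steroid-free state after the taper. The SAP's defining sentence compares with Week 0, when they were on up to 30 mg/day of prednisone or equivalent. A flare treated by going back to that dose, or below it, passes the test as if nothing had changed.

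MCS remission (project SAP, Table 3) has no steroid-free condition. A patient in remission at Week 62 with the help of restarted steroids could therefore be a primary-endpoint success under the SAP sentence and a failure under Protocol 6.4. Two programmers could code this differently in good faith, and an estimand rule should not leave that open.

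**Working it through.** **1. One patient, each text in turn.** The patient is on 30 mg/day at baseline, responds at Week 10, tapers to zero, later restarts oral steroids for UC at no more than 30 mg/day, and meets the MCS remission criteria at Week 62.

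| Text | Test | Result |
|---|---|---|
| SAP 4.4 with SAP 2.2 | Increased over Week 0? No. New since Week 0? No. | Not rescued; can be a remitter |
| SAP Appendix 3 | Initiation? Arguable. Escalation beyond baseline dose? No. | Unclear |
| Protocol 6.4 | Started a corticosteroid for UC in maintenance? On the natural reading, yes. | Non-responder |
| Protocol 3.1.1.2 | Back to baseline dose during the taper? No, after it. | Exemption does not apply |

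**2. How long the gap is open.** Protocol 3.1.1 reduces the dose by 5 mg a week down to 10 mg, then by 2.5 mg a week.
- From 30 mg: (30 − 10)/5 = 4 weeks, then 10/2.5 = 4 weeks, 8 weeks in all. Week 10 + 8 = Week 18.
- Remaining time to Week 62: 62 − 18 = 44 of the 52 maintenance weeks. A lower entry dose reaches zero sooner and leaves longer.

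**3. What the planned analyses would show.**
- The analysis that includes data collected on rescue therapy (SAP 4.4.5) changes nothing for a patient never classed as rescued. The patient is counted as observed there and in the primary analysis.
- Corticosteroid-free remission (SAP 4.4.2.2) requires no steroid record from the Week 62 visit minus 168 days. 168/7 = 24 weeks, so the look-back starts at Week 38. The project SAP (4.4.3) also reports the primary endpoint by baseline steroid use. A restart continuing past Week 38 would therefore appear in the gap between remission and corticosteroid-free remission among baseline steroid users. That gap also contains patients who never finished the taper, so it is an upper bound on restarts and not a count.
- A restart begun and stopped between Week 18 and Week 38 (38 − 18 = 20 weeks) would show nowhere.

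**4. Scale that needs no rate.** The plan's own figure comes first: 105 per arm, two-sided 5% chi-squared test, placebo 30–45%, difference 25 points (SAP 2.3.1; Protocol 6.1). With p̄ the mean of the two rates,

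power = Φ{[d√n − 1.96√(2p̄(1−p̄))] / √(p₁(1−p₁) + p₂(1−p₂))}.

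At 30% versus 55% this is Φ(1.76) = 96.1%. Over the placebo range it is 95.7–96.1%, so the stated >90% reproduces.

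Each patient moved from failure to remission shifts an arm by 1/105 = 0.95 points. For a net excess of k such patients on placebo:
- k = 3: 25 − 300/105 = 22.1 points, power 90.0–90.9%
- k = 4: 25 − 400/105 = 21.2 points, power 87.2–88.4%

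**5. Illustration only; every input is assumed.** Let 40–50% be on steroids at baseline, with restart in 20–30% of them on placebo and 10–15% on etrolizumab, and let 10–50% of restarters be in remission at Week 62. Narrowing = baseline use × (placebo restart × share − etrolizumab restart × share).
- Same share in both arms: from 0.4 × (0.20 − 0.15) × 0.1 = 0.2 points to 0.5 × (0.30 − 0.10) × 0.5 = 5.0 points. With the share held to 10–20%, the maximum is 0.5 × 0.20 × 0.2 = 2.0 points.
- Share differing by arm: from 0.5 × (0.20 × 0.1 − 0.15 × 0.5) = −2.75 points (a widening) to 0.5 × (0.30 × 0.5 − 0.10 × 0.1) = 7.0 points.

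**The case against.** The strongest reply is that one sentence is being read in isolation. The next sentence of SAP 4.4 refers to the protocol and Appendix 3. Appendix 3 makes initiation a trigger with no dose test, and Protocol 6.4 does the same. A programmer who follows those texts would class the restart as rescue. This stands as far as it goes: the SAP is ambiguous, and a reader who infers that it will certainly count restarts as remission goes further than the documents allow. It does not remove the point. The sentence that defines rescue gives the opposite answer, and the appendix mentions the taper without saying what follows it.

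A reader might also infer that no planned analysis could reveal the problem. That is too strong, because later restarts leave a trace in the baseline-steroid subgroup. The restarts that escape entirely are those finished before Week 38 in patients then off steroids for 24 weeks, arguably the least troubling ones.

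A third reply is that the threshold of more than 10 mg for 5 days or longer in Protocol 3.1.1.2 could define a countable restart, so counting any dose is a preference. But that text sits with the choice between staying in the blinded phase and entering the open-label extension, while the outcome rule in Protocol 6.4 has no threshold. Counting any dose is the version consistent with 6.4.

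Finally, a reader might see an equally serious conflict over 5-ASA. Protocol 6.4 names 5-ASA starts as failure only in induction, whereas Appendix 3 carries them into maintenance. The documents do not support treating this as more than a missing declaration. Protocol 3.1.1.2 and 4.3.2.2 discuss maintenance 5-ASA under a rescue heading, so the SAP's choice is defensible. The on-rescue supplementary analysis already bounds the effect: in each arm, the rate under Protocol 6.4 lies between the primary and supplementary rates.

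**Conclusion.** The point holds for steroid restarts. As written, the SAP's defining sentence leaves a patient who restarts corticosteroids for UC after a completed taper, at or below the entry dose, outside rescue. That contradicts Protocol 6.4 and the during-taper limit in Protocol 3.1.1.2, and Appendix 3 does not clearly resolve it. Whether the sentence would be programmed literally cannot be known from the documents.

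Size is unknown. The documents give no restart rate, no share on steroids at baseline, and no remission share among restarters. A net placebo excess of 3 patients leaves power at about 90%; 4 takes it below. In the illustration, the same-share setting with 10–20% in remission gives at most 2.0 points, about 2 patients.

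A reader might infer that the gap favours etrolizumab. Nothing in the documents shows that. If restarts are commoner on placebo and restarters remit at similar rates in both arms, the error narrows the difference and works against etrolizumab. It can go the other way only under different assumptions. The case for acting is that the primary endpoint's failure rule should have one reading, and that giving it one is cheap.

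**What to change.** Before unblinding, state in SAP 4.4 and in the maintenance row of Appendix 3:
- any corticosteroid restarted for UC after a completed taper is an initiation and counts as rescue, whatever the Week 0 dose;
- an increase up to the baseline dose during the taper does not count as rescue.

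This concerns outcome classification only and changes nothing in patient care. The cost is a few sentences and a matching line in the programming; concomitant medication is already recorded at every scheduled treatment visit.

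As a documentation note, add one sentence declaring that counting maintenance 5-ASA starts as rescue goes beyond the maintenance list in Protocol 6.4, while agreeing with Protocol 3.1.1.2 and 4.3.2.2. The SAP already declares other departures in this way (SAP 2.2: "The efficacy outcome measures listed below deviate from the current Study GA29102 Protocol Version 7"; also SAP 4.1.2.1). A sensitivity run that does not count 5-ASA starts as failure is optional.

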#### 4.4.1 Primary Efficacy

##### 4.4.1.1 Primary Treatment Effect

The primary efficacy treatment effect (estimand) targeted is described by the following four attributes:

- a) **Population:** Adult patients with moderate to severe active UC who are naive to TNF inhibitors
- b) **Variable:** Remission at Week 62 given the patient is an etrolizumab-induction phase clinical responder at Week 10.

**c) Intercurrent Event (ICE):**

- Treatment discontinuation
- Use of rescue therapy

Details of the ICE strategy are explained in Section 4.4.

**d) Population-Level Summary:** Difference in proportion of patients between etrolizumab and placebo treatment groups in the Maintenance Phase.

#### **4.4.1.2 Primary Efficacy Endpoint**

The primary efficacy endpoint is the difference in the proportion of patients in remission at Week 62 between the etrolizumab and placebo patients who achieved clinical response at Week 10.

**Proportion of patients in remission at Week 62 among clinical responders at Week 10**

$$= \frac{\text{\# of patients in remission at Week 62}}{\text{\# of patients in Maintenance mITT}}$$

The calculation will be done within treatment groups. Comparisons will only be made between the etrolizumab patients and placebo patients included in the mITT population.

**Null hypothesis H0:**  $\rho_{\text{Etro}} - \rho_{\text{PBO}} = 0$ ; the proportion of patients achieving remission at Week 62 among clinical responders at Week 10 in the placebo arm is the same as the proportion of patients achieving remission among clinical responders in the respective etrolizumab arm.

**Alternative hypothesis H1:**  $\rho_{\text{Etro}} - \rho_{\text{PBO}} \neq 0$ ; the proportion of patients achieving remission at Week 62 among clinical responders at Week 10 in the placebo arm is not the same as the proportion of patients achieving remission among clinical responders in the respective etrolizumab arm.

#### **4.4.1.3 Remission Among Clinical Responders Definition**

Details of remission and clinical responder definition are provided in the project SAP, Section 4.4.2.1.4.

### **4.4.2 Secondary Efficacy Endpoints**

[figure not shown]
#### **4.4.2.1 Control of Type I Error**

The primary and key secondary endpoints (Figure 2) will be evaluated in a hierarchical manner with multiplicity control via multistage gatekeeping under the truncated Holm multiple testing procedure (Dmitrienko et al. 2008). In Families 1 and 2 of the key secondary endpoints the same truncation value of 0.5 will be applied; no truncation is applied in Family 3, since it is prioritized lowest in the hierarchy and imposes no gatekeeping restrictions on subsequent families. The truncation parameter value and the relative effect sizes of the endpoints influence how power is balanced over the secondary endpoint families. Truncation parameter values close to 1 should generally

be chosen when the effect sizes in high-priority endpoints are relatively large in order to maximize overall power. In other settings where the effect sizes might be smaller or mixed, a truncation parameter value closer to 0 could improve overall power. A parameter value strictly less than one in testing families that impose parallel gatekeeping (i.e. at least one endpoint is considered statistically significant after multiplicity adjustment in order to test the next family) is needed to achieve strong overall type I error control (Dmitrienko et al. 2009).

Under this multistage gatekeeping approach, multiplicity-adjusted p-values will reflect the gatekeeping restrictions depicted in Figure 2. In particular, the adjusted p-values for all key secondary endpoints in Families 1, 2, and 3 will be no smaller than the p-value for the primary endpoint. Similarly, the smallest adjusted p-value in Family 2 (3) will be no smaller than the smallest adjusted p-value in Family 1 (2). Endpoints for which the multiplicity-adjusted p-value is greater than 5% will not be considered statistically significant. These endpoints and all endpoints not under multiplicity control will be considered to provide supportive information. By repeated application of Proposition 4.1 of Dmitrienko et al. (2008), this testing strategy ensures that the overall type I error is no greater than 5%.

**Figure 2 Multiple Testing Procedure for Endpoints**

RB=rectal bleeding; SF=stool frequency; UC-PRO/SS=Ulcerative Colitis Patient-Reported Outcome Signs and Symptoms.

Ordering of endpoints within a family will be based on the p-value results from the hypotheses tests of the endpoints in Figure 2.

#### **4.4.2.2 Corticosteroid-Free Remission at Week 62 (Off Corticosteroid for At Least 24 Weeks Prior to Week 62) in Patients Who Were Receiving Corticosteroids at Baseline**

This analysis will only be conducted on a subgroup of patients who were receiving corticosteroids at baseline as per the data collected in electronic Case Report Form (e-CRF) database and were enrolled into the Maintenance Phase. Remission is determined by the MCS defined in the project SAP, Section 4.4.2.1.4. Patients are defined as being off CS if they have no record of taking CS since the date which is 24 weeks prior to Week 62. This date is defined as the Week 62 visit date–168 days.

**Proportion of patients in corticosteroids free remission at Week 62  
(off corticosteroid for at least 24 weeks prior to Week 62)  
in patients who were receiving corticosteroids at baseline**

$$= \frac{\text{\# of patients in remission at Week 62 \& off CS for 24 weeks prior to Week 62}}{\text{\# of patients receiving CS at Baseline in the maintenance mITT}}$$

